9 INVESTIGATIONAL PLAN

9.1 Overview

The eligibility criteria for this trial will be similar to those used in the RTOG 0525 study (Aldape 2009). Prior to the initiation of TMZ and external beam RT, patients will sign consent and undergo leukapheresis for PBMCs in accordance with **SOP-UFBTIP-131**.

Up to 200 newly diagnosed WHO Grade IV glioma patients will be enrolled in the study. Eligible patients will be randomized, undergo leukapheresis and receive “standard-of-care” radiotherapy concurrent with TMZ under the assumption that approximately 120 patients will be vaccinated according to treatment arm in this placebo controlled, single blinded, randomized Phase II study.

Prior to leukapheresis, patients will be randomized to receive one of three treatment regimens with dose-intensified TMZ treatment at 100 mg/m²/day for 21 days with an allocation ratio of 1:1:1 into one of three arms to receive:

- 1) pp65-shLAMP mRNA DCs with GM-CSF 150 µg (Td skin prep)
- 2) pp65-fLAMP mRNA DCs with GM-CSF 150 µg (Td skin prep)
- 3) Unpulsed PBMCs (saline skin prep)

Randomization will be stratified by;

- Age 69 years old and younger, who will receive dose-intensified adjuvant temozolomide; or 70 years old and older who will receive standard dose adjuvant temozolomide.
- Recursive Partitioning Analysis (RPA) class (III, IV, or V). To determine RPA class, Performance Status (PS) will be determined from KPS conversion using the ECOG comparison scale for patients ≤ 50 years; a Mini-Mental State Examination will be performed at enrollment for patients ≥ 50 years.
- CMV seronegative or seropositive

Within 7 weeks of surgery, patients will undergo standard RT with concurrent TMZ at a target dose of 75 mg/m²/day.

Patients will receive the initial cycle of TMZ 4 (+/- 1) weeks after completing RT. Study drugs will be given intradermally at day 22-24 after the first TMZ cycle and divided equally between both inguinal regions in accordance with **SOP-UFBTIP-128**. All patients will receive Td booster (5 Lf) with vaccine #1 regardless of booster history. Vaccine #2 and #3 will occur at 2 week intervals.

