13.2 Stopping Rules

To continuously monitor vaccine-related toxicity, we will use a one-sided Pocock-type sequential boundary (Ivanova et al. 2005) to repeatedly test whether a maximum acceptable DLT rate $T=14.3\%$ (1 patient in 7) has been exceeded. The sequential boundary will consist of the minimum cumulative number of patients experiencing DLTs per concurrent number of patients enrolled that would result in a rejection of the null hypothesis $T \leq 14.3\%$ and halting of the trial. The sequential boundary will be adjusted so that the overall probability of stopping the trial across the accrual of all 80 patients in the two treatment arms of the trial (i.e. the overall Type 1 error rate) is 0.05 when $T=14.3\%$. If the trial runs to completion without being halted for excessive toxicity, insight into the magnitude of the true DLT rate can be gained by noting that the sequential boundary established for $T=14.3\%$ has a $>80\%$ overall chance of stopping the trial if in fact T is actually greater than 27.1%. The sequential boundary for $T=14.3\%$ and stopping probability 0.05 is displayed in the following table:

N	1	2	3	4	5	6	7	8	9	10	11	12	13	14	15	16	17	18	19	20
PB	-	-	3	4	4	4	4	5	5	5	6	6	6	6	7	7	7	7	8	8
N	21	22	23	24	25	26	27	28	29	30	31	32	33	34	35	36	37	38	39	40
PB	8	8	9	9	9	9	9	10	10	10	10	11	11	11	11	11	12	12	12	12
N	41	42	43	44	45	46	47	48	49	50	51	52	53	54	55	56	57	58	59	60
PB	12	13	13	13	13	13	14	14	14	14	15	15	15	15	15	16	16	16	16	16
N	61	62	63	64	65	66	67	68	69	70	71	72	73	74	75	76	77	78	79	80
PB	16	17	17	17	17	17	18	18	18	18	18	19	19	19	19	19	20	20	20	20

N = Number of patients enrolled

PB = Pocock boundary, the minimum cumulative number of patients experiencing vaccine-related toxicity that should stop the trial when the concurrent number of patients enrolled in the trial is **N**

The safety monitoring rule described for vaccine-related toxicity was derived using methods described by Ivanova et al. (Ivanova A, BF Qaqish, and MJ Schell, 2005. Continuous toxicity monitoring in phase II trials in oncology. *Biometrics* 61: 540-545). Pocock boundaries were calculated using an online calculator maintained by one of the authors at the UNC Lineberger Comprehensive Cancer Center website:

(<http://cancer.unc.edu/biostatistics/program/ivanova/ContinuosMonitoringForToxicity.aspx>).

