13.3 Adverse Events

An AE is any untoward medical occurrence associated with use of a drug, whether or not considered drug related. For this protocol, the definition of AE also includes worsening of any pre-existing medical condition. An AE can therefore be any unfavorable and unintended or worsening sign (including an abnormal laboratory finding), symptom, or disease temporally associated with the use of the study drug, whether or not related to use of the study drug. Abnormal laboratory findings without clinical significance (based on the PI's judgment) should not be recorded as AEs. But laboratory value changes that require therapy or adjustment in prior therapy are considered adverse events. Elective and semi-elective surgery in asymptomatic patients should not be recorded as AEs.

An adverse drug reaction is any adverse event caused by a drug. A suspected adverse reaction means any adverse event for which there is a reasonable possibility that the drug caused the adverse event. For the purposes of IND safety reporting, "reasonable possibility" means there is evidence to suggest a causal relationship between the drug and the adverse event.

AE collection will begin at the time of administration of vaccine #1 and continue until 30 days after the last dose of study drug. Grade 2 suspected adverse reactions and all Grade 3 or greater AEs must be recorded in the subject's research record and entered into the OnCore eCRF within 72 hours of PI discovery/notification of the event. Any Grade 3 or greater adverse events associated with leukapheresis will also be recorded. AEs must also be reported to the Coordinating Center as described in 13.3.

AEs will be assessed according to the CTCAE version 5.0 (term and grade) and documented. If CTCAE term does not exist, the PI should select the most appropriate CTC category and indicate "other". If CTCAE grading does not exist for an AE, the severity of the AE will be graded as (1) mild, (2) moderate, (3) severe, (4) life-threatening, or (5) fatal.

Attribution of AEs will be assigned by the PI as follows:

- Definite: The AE is clearly related to the study drug
- Probable: The AE is likely related to the study drug
- Possible: The AE may be related to the study drug
- Unlikely: The AE is doubtfully related to the study drug
- Unrelated: The AE is clearly NOT related to the study drug

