15 STATISTICAL METHODS AND DATA ANALYSIS

15.1 Study Design Overview

The primary goal of this randomized phase II study is to determine whether the addition of pp65-LAMP mRNA DC vaccination in adult patients with newly-diagnosed GBM receiving dose-intensified TMZ will be a treatment worthy of investigation in a large phase III study. A secondary

objective will be examination of the immunologic responses induced by full-length vs short LAMP sequences.

Although this randomized phase II study is comparative, it will not be definitive as the assessment will be conducted with a large false-positive rate. We have included a concurrently followed control arm in the trial design in lieu of a historical control group to ensure that appropriate comparisons can be made without concern that the patients receiving standard treatment differ in prognostic factors or standards of care (Rubinstein, 2009; Ratain and Sargent, 2009; Rubinstein et al., 2005).

We will randomize eligible patients, after enrollment, to one of 3 study arms in which they will receive 21-day TMZ concurrently with one of the following treatments:

Arm #	Vaccine	Skin Preparation
1	pp65-shLAMP mRNA DCs with GM-CSF	Tetanus
2	pp65-fLAMP mRNA DCs with GM-CSF	Tetanus
3	PBMCs	Saline

Randomization will be stratified by:

- Age 69 years old and younger; or 70 years old and older
- RPA Class (III, IV, or V)
- CMV seronegative or seropositive

We will use a permuted block randomization scheme with a 1:1:1 study arm allocation ratio and a block size of 6 within each stratum.

Adapted RPA Stages For Malignant Gliomas (Survival With Concurrent Temozolomide and Radiation Therapy vs Radiation Therapy alone)				
Stage	Characteristics	Median OS	2-year OS	p-value vs. control
III	Age <50, PS 0	21 vs. 15 mo	43% vs. 20%	p<0.0001
IV	Age <50, PS 1-2 Age >=50, Surgery, MMSE >=27	16 vs. 13 mo	28% vs. 11%	p<0.01
V	Age >=50 and either Biopsy only or MMSE <27	10 vs. 9 mo	17% vs. 6%	p=0.05

Approximately 200 patients will be enrolled in the study, randomized and receive “standard-of-care” radiotherapy concurrent with TMZ under the assumption that approximately 120 patients will be vaccinated according to treatment arm.

A Data Sharing Agreement has been established with Immunomic Therapeutics, Inc. and the University of Florida. A Limited Data Set will be sent to evaluate immunogenicity and clinical efficacy of the vaccine products used within this clinical trial (for patients treated at the UF site

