15.2 Sample Size Justification for Vaccine Comparison

The primary focus of this trial will be to assess the worthiness of pp65-LAMP mRNA DC vaccine for further investigation by comparing overall survival (OS) between the active treatment group (Arms 1 and 2 combined) and the control group (Arm 3). Because this test for efficacy will be made within the framework of a phase II trial, we have constrained sample size requirements to yield adequate power to detect a clinically relevant improvement in OS at the expense of the false positive rate (α -level or Type I error rate). Adopting guidelines proposed by Ratain and Sargent (2009) and Rubinstein et al (2005), our proposed sample size of $40 + 40 = 80$ patients in the treatment group and 40 patients in the control group will allow detection of a clinically relevant improvement in the median OS time of the treatment group with 90% power at a one-sided α -level of 0.2.

In determining the effect size that can be detected by our proposed sample size, we considered using as a control reference level the median OS estimate of 14.6 months (95% CI: 13.2 to 16.8) reported by Stupp et al (2005) for patients receiving radiotherapy plus TMZ (RT+TMZ) for newly-diagnosed GBM (40% of patients in the Stupp trial were grossly resected). In the Stupp trial, randomization occurred prior to any post-surgical treatment, and the timing of randomization in our study will be similar. However, in our study, patients will not begin to experience potential differential effects due to treatment until after their first vaccination, which will occur approximately 15 weeks after randomization. To determine an appropriate control reference level for median OS for an index day 15 weeks after randomization, we carefully transferred the coordinates of multiple points along the Stupp RT+TMZ OS curve into a statistical software package. We determined that median OS relative to a starting time 15 weeks after the Stupp index day would be 13.8 months. We also observed that RT+TMZ OS times appeared to approximately follow a Weibull distribution with a shape parameter = 1.20, indicating a slightly accelerating baseline hazard function. Upon examining in a similar manner the RT+TMZ OS curve reported in the paper by Gilbert et al (2013), we also observed approximately Weibull-distributed OS times with shape parameter = 1.16.

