15.3 Analytic Methods

15.3.1 Primary Objective and Secondary Clinical Objectives

We will use Kaplan-Meier survival curves and the log rank test to characterize and compare PFS and OS in patients who received pp65-LAMP mRNA DC vaccine (Arms 1 and 2) and in control patients (Arm 3). PFS is defined as the time between first vaccination and first documentation of either disease progression/recurrence, or death without prior progression/recurrence. Patients remaining alive without disease progression will have PFS censored at last follow-up. OS will be defined as the time between first vaccination and death, and will be censored at the last follow-up if death has not occurred. We will also perform a stratified analysis incorporating the three stratification variables (age, RPA class, and CMV sero-status) using Cox proportional hazards regression. The index day for all of our primary comparisons will be the time of the first vaccination. Because patients who fail to proceed to the first vaccination because of GBM recurrence or for other reasons cannot experience differential effects due to treatment arm membership, we will not perform an intent-to-treat analysis that includes these patients. We will perform an intent-to-treat analysis of OS and PFS that includes patients who begin the vaccination sequence but who do not receive at least three vaccinations because of recurrence or other reasons. OS and PFS times for adequately vaccinated patients who are lost to follow-up will be considered right-censored at the time of loss and will be included in all of our survival comparisons.

All subjects who receive at least one dose of DC vaccine will be considered evaluable for purposes of safety and toxicity.

All subjects who complete chemoRT and receive dose-intense adjuvant TMZ and at least 3 DC vaccines will be considered evaluable for purposes of the primary and secondary endpoints.

The impact of pp65-LAMP mRNA DC vaccine on PFS and OS in patients with gross total resection will also be explored using the log rank test and Kaplan-Meier curves, although our trial design may not necessarily achieve sufficient power to detect a clinically meaningful effect within this patient subgroup.

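### The DLT stopping table in Section 13.2 counts patients enrolled, but its stated error rates hold only if N counts DC-vaccinated patients in Arms 1 and 2

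*Combined protocol and SAP*

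**What the plan says.** Section 13.2 sets up a one-sided Pocock-type boundary to test whether the DLT rate exceeds 14.3% (1 in 7). The rule sentence describes the boundary as "the minimum cumulative number of patients experiencing DLTs per concurrent number of patients enrolled". The legend under the table gives N as the number enrolled, and the boundary entry is defined as "the minimum cumulative number of patients experiencing vaccine-related toxicity that should stop the trial when the concurrent number of patients enrolled in the trial is" a given row number. The 0.05 overall error is set "across the accrual of all 80 patients in the two treatment arms of the trial", and the table ends at row 80 with a boundary of 20. The section also states a better than 80% chance of halting if the true rate is above 27.1%.

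Other sections show that enrolled and DC-vaccinated patients are different groups:

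- Section 15.1: "Approximately 200 patients will be enrolled in the study, randomized and receive" chemoradiation, allocated 1:1:1.
- Section 9.1: this is done "under the assumption that approximately 120 patients will be vaccinated according to treatment arm". Section 15.2 splits the 120 into 80 treated and 40 control.
- Section 15.2: differential effects begin only "after their first vaccination, which will occur approximately 15 weeks after randomization".
- Section 13.3: "AE collection will begin at the time of administration of vaccine #1".
- Section 15.3.1: "All subjects who receive at least one dose of DC vaccine will be considered evaluable for purposes of safety and toxicity". Section 9.8 likewise applies the DLT stopping rules to anyone given DC vaccine.

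**The concern.** An enrolled patient who has not yet been vaccinated, or never will be, adds one to N but cannot add a DC-vaccine DLT. On the literal wording, control patients also add to N. Every such patient moves the reader along the table to a row that may demand more DLTs before a halt, so the error always runs in the unsafe direction.

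This is the plan's only numeric trial-level boundary for vaccine toxicity, and whoever applies it will take N from the legend. Section 13.2 also invites the reader to infer something about the true DLT rate if the trial runs to completion without a halt. That inference is valid only if N counted DC recipients.

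**Working it through.** **Method.** Let each patient counted in N have DLT probability p = f × T, where T is the true DLT rate among DC recipients and f is the share of counted patients who receive DC vaccine. Step through N = 1 to 80, updating the binomial distribution of the cumulative DLT count exactly. At each row, move to the stopped state any probability at or above the printed boundary. P(stop) is the total removed.

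**Step 1: reproduce the plan (f = 1).**
- T = 0.143: P(stop) = 0.0472 (stated 0.05; the boundary is discrete).
- T = 0.271: P(stop) = 0.7995. It reaches 0.80 at T = 0.2711, which matches the stated figure.
- A constant pointwise binomial level of 0.01044 at 0.143 regenerates all 80 printed cells. The table is therefore correct for 80 patients who are all at risk.

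**Step 2: the share at risk under the printed label.**
- N = Arm 1 and 2 enrollees: f = 120/200 = 0.60, so p = 0.60 × 0.271 = 0.1626.
- N = all enrolled: f = 80/200 = 0.40, so p = 0.40 × 0.271 = 0.1084. Controls are assumed to contribute no DC-vaccine DLT.
- The 120/175 case uses the earlier enrollment estimate in the amendment log: 120/175 = 0.686 and 80/175 = 0.457.

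**Step 3: results on the 80 printed rows, no lag.**

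| Count used for N | f | P(stop) at T = 27.1% | T needed for 80% | DC recipients at row 80 | 20 DLTs as a share of them |
|---|---|---|---|---|---|
| DC-vaccinated, Arms 1 and 2 | 1.00 | 0.7995 | 27.1% | 80 | 25.0% |
| Arm 1 and 2 enrollees, 120/200 | 0.60 | 0.100 | 45.2% | 48 | 41.7% |
| All enrolled, 120/200 | 0.40 | 0.010 | 67.8% | 32 | 62.5% |
| Arm 1 and 2 enrollees, 120/175 | 0.686 | 0.208 | 39.5% | 54.9 | 36.5% |
| All enrolled, 120/175 | 0.457 | 0.021 | 59.3% | 36.6 | 54.7% |

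**Step 4: the 15-week lag.** The documents give no accrual rate by arm, so this is an assumption. 15 weeks is about 3.45 months.
- Lower case: 132 × 2/3 ÷ 48 × 3.45 ≈ 6 Arm 1 and 2 enrollees awaiting vaccine.
- Upper case: 200 × 2/3 ÷ 36 × 3.45 ≈ 13.
- With f = 0.60, the 0.100 becomes 0.043 or 0.031 if late DLTs are still set against row 80, and 0.032 or 0.008 if monitoring ends at the 80th enrollee.

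**Step 5: monitoring past row 80.** The plan gives no rule for this. Two possible continuations at T = 27.1%, no lag:
- Hold the last value (20) through all enrollment: 0.69 for Arm 1 and 2 enrollees (to 133) and 0.68 for all enrolled (to 200).
- Extend at the same pointwise level: 0.137 and 0.010.

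**Step 6: more than 80 DC recipients.** Section 9.8 replaces patients who do not meet its evaluable definition but keeps them under the stopping rules, so DC recipients can exceed 80. Extending at level 0.01044 gives 20 at row 81, 21 at rows 82–87 and 22 at rows 88–91. Overall error at 14.3% is then 0.0497 at 91, 0.0501 at 92 and 0.0516 at 100.

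**The case against.** The strongest reply is that the intended N is clear. Section 13.2 ties its error rate to 80 patients in two arms, Section 15.2 shows that 80 is the planned treated number, and Sections 9.8 and 15.3.1 tie toxicity monitoring to DC recipients. This stands as evidence of intent, and it makes the all-enrolled reading the less plausible one. It does not correct the legend, and the two-arms clause does not exclude unvaccinated Arm 1 and 2 enrollees, so the 0.100 reading survives it.

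Second, the table speaks of vaccine-related toxicity, and the control PBMC injection is also called a vaccine, so 0.010 is a floor for the all-enrolled reading. That is fair. If controls had DLTs at the same 27.1%, f would be 120/200 = 0.60 and the answer would be 0.100, still far below 0.80.

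Third, low power depends on monitoring ending at row 80. Holding 20 DLTs throughout would recover about 0.69. The plan contains no such rule, the figure is still short of 80%, and rows past 80 could trigger a halt only late.

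Fourth, the upper lag case joins 200 enrollees to the 3-year accrual assumed for 120, faster than the 132 enrolled after more than four years. That is correct; it is a bounding assumption and the conclusion does not need it.

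Fifth, other safeguards exist: per-patient DLT rules, suspension after certain deaths, and oversight by the data and safety committee. The December 2020 log entry reports 2 related Grade 3 or greater events with 132 enrolled, below the lowest boundary value of 3. No halt had been missed by then on any count. Later counts are not given.

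**Conclusion.** The concern holds. As written, the rule does not have the stopping probabilities that Section 13.2 claims for it. At a true DLT rate of 27.1%, the chance of halting is 0.100 if N is Arm 1 and 2 enrollees and 0.010 if N is all enrolled, against the stated 80%. At the earlier 120/175 estimate the figures are 0.208 and 0.021. They assume a constant share vaccinated, 1:1:1 allocation, the printed 80 rows, no lag and, for the all-enrolled figures, no control DLTs. The most favorable continuation examined, which the plan does not contain, gives 0.68 to 0.69.

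The boundary values themselves are sound; the fault is the definition of N. It should be fixed. The possibility of more than 80 DC recipients is secondary, since the documents do not say whether it occurred.

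**What to change.** In the rule sentence, the N legend and the boundary definition of Section 13.2, define N as the cumulative number of patients in Arms 1 and 2 who have received at least one DC vaccine, including those vaccinated under Section 9.8. Count DLTs in the same patients.

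Also state what applies beyond row 80. If no more than 91 DC recipients are expected, append the 11 rows in Step 6; no printed row changes and overall error stays at 0.0497. For a larger maximum, choose one of two routes:

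- Recompute to keep error at or below 0.05. For a maximum of 100 or 110, rows 7, 27, 46 and 61 each rise by one, with error 0.0478 or 0.0497.
- Extend at the same pointwise level and restate the overall error, about 0.052 at 100.

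The cost is a wording change in three places plus the appended rows. Sample size and the 14.3% rate are unaffected, and so are the printed boundary values up to 91 DC recipients. If the trial has finished, report which count was used for N before drawing any conclusion from the absence of a halt.

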13.3 Adverse Events

An AE is any untoward medical occurrence associated with use of a drug, whether or not considered drug related. For this protocol, the definition of AE also includes worsening of any pre-existing medical condition. An AE can therefore be any unfavorable and unintended or worsening sign (including an abnormal laboratory finding), symptom, or disease temporally associated with the use of the study drug, whether or not related to use of the study drug. Abnormal laboratory findings without clinical significance (based on the PI's judgment) should not be recorded as AEs. But laboratory value changes that require therapy or adjustment in prior therapy are considered adverse events. Elective and semi-elective surgery in asymptomatic patients should not be recorded as AEs.

An adverse drug reaction is any adverse event caused by a drug. A suspected adverse reaction means any adverse event for which there is a reasonable possibility that the drug caused the adverse event. For the purposes of IND safety reporting, "reasonable possibility" means there is evidence to suggest a causal relationship between the drug and the adverse event.

AE collection will begin at the time of administration of vaccine #1 and continue until 30 days after the last dose of study drug. Grade 2 suspected adverse reactions and all Grade 3 or greater AEs must be recorded in the subject's research record and entered into the OnCore eCRF within 72 hours of PI discovery/notification of the event. Any Grade 3 or greater adverse events associated with leukapheresis will also be recorded. AEs must also be reported to the Coordinating Center as described in 13.3.

AEs will be assessed according to the CTCAE version 5.0 (term and grade) and documented. If CTCAE term does not exist, the PI should select the most appropriate CTC category and indicate "other". If CTCAE grading does not exist for an AE, the severity of the AE will be graded as (1) mild, (2) moderate, (3) severe, (4) life-threatening, or (5) fatal.

Attribution of AEs will be assigned by the PI as follows:

- Definite: The AE is clearly related to the study drug
- Probable: The AE is likely related to the study drug
- Possible: The AE may be related to the study drug
- Unlikely: The AE is doubtfully related to the study drug
- Unrelated: The AE is clearly NOT related to the study drug

An adverse event is considered a Serious Adverse Event if it results in any of the following outcomes: 1) fatal or life threatening; 2) inpatient hospitalization or a prolongation of existing hospitalization; 3) a significant, persistent or permanent change, impairment, damage or disruption in the patient's body function/structure, physical activities and/or quality of life; 4) congenital anomaly or a birth defect and/or; 5) medically significant such that it may jeopardize the subject, and may require medical or surgical intervention to prevent one of the outcomes listed above.

An unexpected adverse event or unexpected suspected adverse reaction is an adverse event or suspected adverse reaction that is not listed in the investigator brochure or is not listed at the specificity or severity that has been observed or is not consistent with the risk information described in the general investigational plan or elsewhere in the IND application (if there is no investigator brochure).

A summary of all Grade 3 or greater adverse events (not just those considered related to the vaccine) will be maintained. Events will be categorized by organ system, relationship to treatment, grade or severity, and outcome. The Protocol Chair will periodically review the adverse event summary with the intention of identifying any trends or patterns in toxicity. If any such trends are identified, depending on their severity, frequency, and timing with respect to treatment, the Protocol Chair may request that the events be evaluated by a convened data safety monitoring board.

